## **Title of Study:**

A Dose-escalation Study to Detect Urease-producing Bacteria in Lungs of Healthy Volunteers and Subjects with Cystic Fibrosis Using Aerosolized C-urea

**Indication:** Use of a C-urea breath test in the qualitative detection of urease-containing bacteria in the respiratory tract and as an aid in the initial and post-treatment detection of respiratory tract infections

**Study Design:** This is a single-center, single-administration, dose-escalation study designed to determine the safety and dose response of aerosolized C-urea 20 mg and 50 mg in detecting urease-producing bacteria in the lungs of healthy volunteers (those without and those diagnosed with *Helicobacter pylori* infection) and in subjects with cystic fibrosis (CF). Subjects will be contacted by telephone the next day and asked a non-leading question about adverse events.

The dose will not be escalated until at least 24 hours after all subjects in the cohort have been tested at the current dose. If a subject has an adverse event or new symptom that remains unresolved at 48 hours, no new subjects will be enrolled until the relationship between the AE and symptom can be evaluated. If any subject experiences an adverse event considered by the data safety monitor to be dose limiting, then three additional subjects will be enrolled at that current dose. Dose escalation will stop if more than one additional subject experiences dose-limiting toxicity.

After the safety of the maximum dose in the cohort of healthy volunteers without *H. pylori* infection has been reviewed by a data safety monitor, healthy volunteers diagnosed with *H. pylori* infection and subjects with CF will be enrolled. Three subjects diagnosed with *H. pylori* infection will be tested at the maximum dose to assess potential interference of urease producing bacteria in the stomach; subjects infected with *H. pylori* can be enrolled at any time after the safety of the maximum dose in healthy volunteers without *H. pylori* infection has been evaluated, but they will meet the entrance criteria for healthy volunteers without *H. pylori* infection.

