# Study Product, Dose, and Mode of Administration:

C-urea: 20 mg and 50 mg administered by inhalation

Reference Product, Dose, and Mode of Administration: Not applicable

**Efficacy Variables:** Breath test results

**Safety Variables:** Adverse events (frequency, intensity, seriousness, and relationship to study drug), spirometry test results (FEV1 and FVC), and respiratory examinations (respiratory rate, auscultation [presence of wheezing and crackles], pulse oximetry, and related symptoms, such as cough)

**Pharmacokinetics:** Production of carbon dioxide

**Sample Size and Statistical Rationale:** Approximately 15 subjects will be enrolled, 9 healthy volunteers and 6 subjects with CF. Three healthy volunteers without *H. pylori* infection will each receive

Location of study: University of New Mexico Hospital, Pediatric/Adult Pulmonary Clinic, Ambulatory Care Center, Albuquerque, NM  Finished product:  13C-urea Breath Test Kit		Tabulated Study Protocol	
Active ingredient:  13C-urea			
Protocol date HRPO# 29 November 2012 12-521		Planned study period January 1, 2013-March 31,2013	

a single 20 mg dose and 3 will each receive a single 50 mg dose. After the safety of the 50 mg dose has been evaluated, 3 subjects with CF will each receive a single 20 mg dose and 3 subjects with CF will each receive a single 50 mg dose. Three healthy volunteers diagnosed with *H. pylori* infection will also each receive a 50 mg dose to assess potential interference of urease producing bacteria in the stomach. Three additional subjects will be added to every dose level at which a dose-limiting adverse event occurs; no more than 30 subjects will be enrolled. This sample size is based upon a dose-escalation model, not a calculation of statistical power.

**Study Sites and Location:** The study will be conducted at a single center at the University of New Mexico Hospital, Pediatric/Adult Pulmonary Clinic, Ambulatory Care Center, Albuquerque, NM.

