# 3.1.3 Study Design

This is a single-center, single-administration, dose-escalation study designed to determine the safety and dose response of aerosolized C-urea 20 mg and 50 mg in detecting urease-producing bacteria in the lungs of healthy volunteers (those without and those diagnosed with *H. pylori* infection) and in subjects with CF. Subjects will be contacted by telephone the next day and asked a non-leading question about adverse events.

The dose will not be escalated until at least 24 hours after all subjects in the cohort have been tested at the current dose. If a subject has an adverse event or new symptom that remains unresolved at 48 hours, no new subjects will be enrolled until the relationship between the AE and symptom can be evaluated. If any subject experiences an adverse event considered by the data safety monitor to be dose limiting, then three additional subjects will be enrolled at that

current dose. Dose escalation will stop as described in Table 1 if more than one additional subject experiences dose-limiting toxicity (DLT) (Section 3.1.3.1).

After the safety of the maximum dose in the cohort of healthy volunteers without *H. pylori* infection has been reviewed by a data safety monitor, healthy volunteers diagnosed with *H. pylori* infection and subjects with CF will be enrolled. Three subjects diagnosed with *H. pylori* infection will be tested at the maximum dose to assess potential interference of urease producing bacteria in the stomach; subjects infected with *H. pylori* can be enrolled at any time after the safety of the maximum dose in healthy volunteers without *H. pylori* infection has been evaluated, but they will meet the entrance criteria for healthy volunteers without *H pylori* infection. Subjects will be discharged from the study site after 30 minutes or thereafter when oxygen saturation levels and FEV1 values return to baseline and coughing symptoms are resolved. Supportive treatment for symptom resolution, if needed, will be recorded on the case report form (CRF).

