**Table 1 Dose Escalation Rules** 

Condition within 24 hours after administration of study drug	Number of DLTs/ Subjects in Cohort	Action
If no subject experiences DLT	0/3	Enroll three subjects at the 50 mg dose level
If one subject experiences DLT	1/3	Enroll three additional subjects at the 20 mg dose
If no additional subject experiences DLT	1/6	Enroll three subjects at the 50 mg dose level
If more than one subject experiences DLT	>1/6	Stop enrollment

Subjects will be receive C-urea 20 mg and 50 mg unless enrollment stops because of DLT. DLT Dose-limiting toxicity.

Sputum will be collected from each subject with CF before administering study drug in order to identify bacterial flora using two standard microbiologic methods. The first is a quantitative method in which colonies are stained and counted, the second is a colorimetric method in which a sample is plated in a medium that changes to a blue color as its pH is increased by the production of ammonia, a by-product of the urease-catalyzed degradation of urea.

The pharmacokinetics of the production of C-carbon dioxide will be characterized by determining the isotopic ratio of C to C in exhaled carbon dioxide of subjects in each part before study drug administration and at 5, 10, and 15 minutes.

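### Table 1 covers only the 20 mg step, and the protocol's rules for dose-limiting toxicity at 50 mg disagree on trigger, consequence and MTD

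*Protocol*

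**What the plan says.** **Table 1.** With no DLT in three subjects, or one in six, the action is to enroll three at 50 mg. With one in three it is "Enroll three additional subjects at the 20 mg dose". With more than one, enrollment stops; that row names no dose. The footnote says subjects receive "20 mg and 50 mg unless enrollment stops because of DLT". Section 5.1.8 refers to the table for both the 20 mg and the 50 mg cohort.

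**Expansion.** Section 3.1.3 adds three subjects at the current dose. The synopsis says "Three additional subjects will be added to every dose level at which a dose-limiting adverse event occurs; no more than 30 subjects" will be enrolled; 3.2.1 and 9.1 agree.

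**Stopping.** The synopsis says "Dose escalation will stop if more than one additional subject experiences dose-limiting toxicity". Section 3.1.3 has the same trigger but refers to Table 1. Section 3.2.3 stops escalation if more than one subject has a DLT at any dose level, and adds that the data safety monitor may end enrollment.

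**Later cohorts.** *H. pylori* and CF subjects are enrolled "After the safety of the maximum dose in the cohort of healthy volunteers without" *H. pylori* infection has been reviewed by the monitor (3.1.3). Section 5.1.6 gives *H. pylori* volunteers the MTD. In the synopsis, 3.2.1 and 9.1, three volunteers with *H. pylori* "infection will also each receive a 50 mg dose to assess potential interference", and three CF subjects also receive 50 mg. Section 3.1.3.2 defines the MTD as the dose level given before enrollment was stopped for DLT, or a lower dose if the monitor sees evidence of an adverse safety profile.

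**The concern.** Safety is the primary objective, and Section 1.5 says that this breath test has not been studied in humans before. The DLT rules are therefore the main decision rules of the trial. They should give one answer to three questions at the top dose: how many DLTs count as failure, what then stops, and what dose (if any) later subjects receive. The protocol gives more than one answer to each. In the branch where 50 mg fails in healthy volunteers, the monitor and the site would have to choose between written rules while nine planned subjects are still to be enrolled.

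**Working it through.** **Planned and maximum numbers.** There are five cohorts of three: healthy 20 mg, healthy 50 mg, *H. pylori* 50 mg, CF 20 mg and CF 50 mg. Planned: 5 × 3 = 15. One DLT in each cohort adds 5 × 3 = 15, giving 30. Both match the protocol. The 30 requires that DLTs in the three 50 mg cohorts also trigger expansion, so the rules are meant to run at 50 mg, where Table 1 has no row for them.

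**Sources side by side, for DLTs in the healthy 50 mg cohort.**

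| Question | Table 1 and footnote | Synopsis (design) | 3.1.3 | 3.2.3 |
|---|---|---|---|---|
| Trigger | more than one subject | more than one additional subject | more than one additional subject | more than one subject |
| Is 2/6 (one in the first three, one in the next three) a failure? | yes | no | no as worded; yes if Table 1 governs | yes |
| Consequence | enrollment stops | escalation stops | escalation stops, with reference to Table 1 | escalation stops; monitor may stop enrollment |

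No dose lies above 50 mg, so stopping escalation has no effect within that cohort. It does not touch the *H. pylori* cohort either, which involves no escalation. It could bear on the CF step from 20 to 50 mg only if a stop in healthy volunteers carries over to the CF part, and no sentence says so.

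**MTD.** The first limb of 3.1.3.2 can mean the dose in use when enrollment stopped (50 mg) or the level before it (20 mg). It also presupposes that enrollment stopped, yet 5.1.6 uses it to dose *H. pylori* volunteers who enroll afterwards.

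**Subjects affected.** By then 3 to 6 subjects have been treated at 20 mg and 3 to 6 at 50 mg, so 6 to 12 in all. If enrollment ends, the total stays at 6 to 12. If it continues, the other 9 planned subjects (3 *H. pylori*, 6 CF) bring it to 15 to 21 before any further expansion. Of those 9, 3 + 3 = 6 are planned at 50 mg.

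**Chance of reaching the unclear branch.** The protocol gives no DLT rate, so the rate p at 50 mg is an assumption. Low values are included because 3.2 does not expect isotonic solutions to cause bronchospasm.

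- More than one DLT in up to six: 1 − [(1−p)³ + 3p(1−p)⁵].
- The disputed 2/6 pattern (one in three, then one in three): [3p(1−p)²]² = 9p²(1−p)⁴.
- Failure under the additional-subject wording: the first minus the second, taking two or more DLTs in the first three as failure under either wording.

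| p | More than one DLT | Disputed 2/6 | Failure under additional-subject wording |
|---|---|---|---|
| 1% | 0.1% | 0.1% | 0.03% |
| 5% | 2.7% | 1.8% | 0.8% |
| 10% | 9.4% | 5.9% | 3.5% |
| 20% | 29.1% | 14.7% | 14.4% |
| 30% | 50.6% | 19.4% | 31.1% |

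Example for p = 10%: 1 − [0.729 + 0.177] = 0.094; 9 × 0.01 × 0.6561 = 0.059; 0.094 − 0.059 = 0.035. These are chances, once 50 mg is reached, of meeting the unclear rule. They are not chances of harm.

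**The case against.** The best defense is that one rule can be assembled from the text. Stopping enrollment necessarily stops escalation, neither the synopsis nor 3.2.3 says that only escalation stops, 3.1.3 refers to Table 1, and the stop row and footnote name enrollment. On this reading more than one DLT ends enrollment. That is plausible, but 3.2.3 then lists ending enrollment as something the monitor may do, and 5.1.6 assigns an MTD defined by an enrollment stop to people enrolled later. The trigger difference also remains, because the synopsis contains no reference to Table 1.

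The monitor's role is a strong mitigating point and stands. The monitor sees data daily and decides when doses rise and subjects enroll (8.5), reviews the maximum dose before the later cohorts (3.1.3), may stop escalation at discretion (3.2), and can set a lower MTD (3.1.3.2). CF subjects also start at 20 mg under the same escalation design (1.5), so the CF 50 mg cohort sits behind a further step.

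Three stronger readings should be resisted:

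- A reader might infer that the protocol requires 50 mg for later subjects even after it fails. It does not: those assignments are the default plan, the Table 1 footnote qualifies them, and the CF cohorts follow an evaluation of 50 mg.
- A reader might infer that a DLT at 50 mg sends the extra three subjects to 20 mg. The current-dose wording in 3.1.3 and the every-dose-level wording elsewhere show that the row is a table error with clear intent.
- A reader might infer that the monitor's review cannot change a dose. The second limb of the MTD definition allows it, though at discretion and, through 5.1.6, expressly only for the *H. pylori* cohort.

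**Conclusion.** The point holds as an inconsistency in the written safety rules. Table 1 is incomplete for 50 mg. The trigger differs between sections, so 2/6 is a failure under Table 1 and 3.2.3 but not under the wording of the synopsis and 3.1.3. The consequence is given as an enrollment stop in one place and an escalation stop in others. The MTD can be read as the failed dose. Followed literally, some of these texts lead to the wrong dosing action.

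The size is moderate. The branch affects 9 planned subjects, 6 of them planned at 50 mg. Its probability is small at low DLT rates (0.1% to 2.7% for 1% to 5%) and substantial only at rates for which the protocol gives no support (29% to 51% for 20% to 30%). Monitor oversight makes an unsafe outcome less likely still. The text should nevertheless be corrected, because this is a safety rule and the correction is cheap. Confidence is medium, since a careful reader could harmonize part of the text around Table 1.

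**What to change.** 1. In Table 1, replace the named doses by the current dose and the next dose, if any.
2. Use one trigger in the synopsis, 3.1.3, Table 1 and 3.2.3: more than one DLT among up to six subjects at a dose level.
3. State that meeting it at 50 mg stops all further 50 mg dosing, including the *H. pylori* and CF 50 mg cohorts.
4. In 3.1.3.2, define the MTD as the highest dose level with no DLT in three subjects or no more than one in six, or a lower dose at the monitor's discretion.
5. Make the 50 mg assignments in the synopsis, 3.2.1 and 9.1 conditional on this.
6. State whether remaining *H. pylori* and CF subjects then continue at 20 mg or enrollment ends. Either is defensible; the protocol should name one.

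The cost is one table, one definition, matching wording and one decision by the sponsor-investigator. The planned 15 subjects, the ceiling of 30, the visits and the procedures do not change.

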# 3.1.3.1 Dose-limiting Toxicity

The following significant respiratory events will be considered DLTs (Rosenfeld et al 2011):

- an absolute decrease from baseline FEV1 of 20% of baseline or greater
- an absolute decrease from baseline oxygen saturation of at least 10%
- an increase from baseline respiratory rate of 10 breaths per minute for more than 2 minutes during quiet breathing
- new wheezes or rales on examination.

In addition to these events that are mandated DLT, the data safety monitor may determine any serious adverse event attributed to study drug to be dose limiting.

### 3.1.3.2 Maximum Tolerated Dose

The maximum tolerated dose is either the dose level administered before enrollment was stopped because of DLT or a lower dose if, in the data safety monitor's opinion, significant evidence exists to reasonably predict an adverse safety profile at that dose for the study drug.

## 3.2 DISCUSSION OF STUDY DESIGN

Aerosolized urea has been studied in doses ranging from approximately 32 mg (Cade and Pain 1972) to approximately over 7000 mg (Waldron-Edward and Skoryna 1966). The present study investigates doses up to 50 mg, which, based upon laboratory studies discussed below, is anticipated to evidence early indication of changes in the number of urease-containing bacteria in the lungs.

Subjects with CF are selected because they have large amounts of urease-producing bacteria in their lungs, are not acutely ill, and are familiar with procedures used in this study. Subjects with CF who are known to be colonized with *Pseudomonas* will be selected because *pseudomonas* has well documented urease activity. It is likely that subjects with CF will have additional lung pathogens that may also contribute to the signal; the breath test is intended to be specific for urease-producing bacteria. Pathogens in sputum cultures from subjects with CF will also be identified and tested for urease activity.

Healthy volunteers diagnosed with *H. pylori* infection are enrolled to determine whether a urease-producing pathogen in the stomach can produce C-carbon dioxide in exhaled breath within 15 minutes after administering study drug by inhalation.

The dose-escalation model minimizes subject risk by incrementally increasing the dose of study drug administered to healthy volunteers, beginning at a dose that approximates 0.1% of one that produced no adverse effects in patients with CF and ending with a dose that approximates the minimum amount administered to patients with asthma.

A maximum dose of 50 mg of C-urea was selected because it can be reconstituted to provide an isotonic solution in a volume that can be inhaled in a sufficiently short time window using a standard nebulizer. The urease reaction is rapid, and the direct delivery of C-urea to the lung

combined with immediate release of C-carbon dioxide enables the production of a signal. Because a 75 mg oral dose of C-urea is sufficient to reliably produce a measurable amount of exhaled C-carbon dioxide in patients infected with stomach *H. pylori*, which requires the carbon dioxide produced by the catalyzed hydrolysis of urea in the stomach to be absorbed into the blood stream and transported to the lung, it is likely that a 50 mg dose administered to the lung directly will produce a reliably measurable signal. The suitability of a lower dose, 20 mg dose, C-urea will also be tested.

In addition to mandatory rules that stop dose escalation in the event of DLT, dose escalation may also be stopped at the discretion of the data safety monitor.

Albuterol is standard therapy for relief of bronchospasm (Eng et al 1996) and also for the prevention of bronchospasm in diseases such as exercise-induced asthma (Raissy et al 2008). Patients with CF are frequently pretreated with albuterol if a therapy may produce bronchospasm, e.g., inhalation of 7% saline. Although nebulized isotonic solutions are not expected to produce bronchospasm, subjects with CF will be pretreated with albuterol because of the potential of mild bronchospasm induced from irritation of lung pathogens at the time of study drug administration.

The characterization of the pharmacokinetics of C-carbon dioxide will inform the useful time interval during which the isotopic ratio of C to C can be measured after administration of study drug in patients with lung infections (Otsuka America Pharmaceutical, Rockville, Maryland). Multiple breath specimens will be obtained at 15 minutes to estimate intra-patient variability.

# 3.2.1 Number of Subjects

Approximately 15 subjects will be enrolled, 9 healthy volunteers and 6 subjects with CF. Three healthy volunteers without *H. pylori* infection will each receive a single 20 mg dose and 3 will each receive a single 50 mg dose. After the safety of the 50 mg dose has been evaluated, 3 subjects with CF will each receive a single 20 mg dose and 3 subjects with CF will each receive a single 50 mg dose. Three subjects diagnosed with *H. pylori* infection will also each receive a 50 mg dose to assess potential interference of urease-producing bacteria in the stomach. Three additional subjects will be added to every dose level at which a dose-limiting adverse event occurs. If one subject at each dose level experiences DLT, then a maximum of 30 subjects will enroll.

## 3.2.2 **Duration of Study**

Subjects will participate in the study for approximately 9 days, up to 7 days between the screening visit and the study visit plus a follow-up visit 24 hours after study drug administration. Subjects will receive a single dose of study drug and remain in the clinic for at 30 minutes for evaluation and observation. Subjects will be discharged from the study site after 30 minutes or thereafter when oxygen saturation levels and FEV1 values return to baseline and coughing symptoms are resolved. Twenty-four hours after administration of study drug, subjects will be contacted by telephone for a safety evaluation by study personnel. If an adverse event is

reported at the telephone contact, the subject will be asked to return to the clinic for an evaluation.

A 24-hour period will separate dose escalations. Thus, the study is anticipated to be completed within approximately 4 to 8 weeks after the first subject enrolls.

# 3.2.3 Premature Termination of Study

Dose escalation will be stopped if more than one subject experiences DLT at any dose level. The data safety monitor may terminate the study early by stopping enrollment based upon safety concerns

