# **5.1.7** Selection of Doses in the Study

Enrolled subjects will receive single doses of C-urea 20 mg or 50 mg.

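### The DLT rules use *dose level* and *cohort* in incompatible senses, so when escalation stops, and whether 30 is the right maximum, depends on an undefined counting unit

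*Protocol*

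**What the plan says.** Table 1 (section 3.1.3) tracks DLTs in a column headed "Number of DLTs/ Subjects in Cohort", with states 0/3, 1/3, 1/6 and more than 1/6. Its action column uses *dose level* for the milligram dose, since it sends three subjects to the 50 mg level. Its last row stops enrolment.

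Section 3.2.3 has a different unit and a different consequence: "Dose escalation will be stopped if more than one subject experiences DLT at any dose level".

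Section 3.2.1, repeated in 9.1, adds three subjects at every dose level with a DLT and concludes: "If one subject at each dose level experiences DLT, then a maximum of 30 subjects will enroll". The synopsis words 30 as a cap.

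On the doses, section 5.1.7 says "Enrolled subjects will receive single doses of 13 C-urea 20 mg or 50 mg". On the groups, section 3.2.1 says:
- Overall: "Approximately 15 subjects will be enrolled, 9 healthy volunteers and 6 subjects with CF"
- Healthy group, not infected: "will each receive a single 20 mg dose and 3 will each receive a single 50 mg dose"
- CF group: "3 subjects with CF will each receive a single 20 mg dose and 3 subjects with CF will each receive a single 50 mg dose"
- *H. pylori* group: "infection will also each receive a 50 mg dose to assess potential interference of urease-producing bacteria in the stomach"

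Section 5.1.8 names only a first cohort at 20 mg and a second at 50 mg. Section 5.1.6 applies Table 1 to subjects without *H. pylori* and gives the *H. pylori* group the maximum tolerated dose. No section defines either term or says whether DLTs at one dose are pooled across populations.

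**The concern.** A stopping rule needs a fixed denominator. Here two doses are spread over five groups, and the rule is written once per cohort and once per dose level. The stated maximum works only with a meaning of *dose level* that differs from the one in Table 1.

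Safety is the primary objective, and section 1.5 calls this the first human study of this breath test. Under section 8.5 the data safety monitor decides when doses rise and when subjects may enrol. If a dose already has one DLT in one population and a second occurs in another, the text supports two opposite actions on the same data: add three subjects, or stop escalating. The planned maximum enrolment depends on the same choice.

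**Working it through.** **Inputs (3.2.1, 5.1.7).** There are five groups of three: healthy 20 mg, healthy 50 mg, CF 20 mg, CF 50 mg and *H. pylori* 50 mg. There are two milligram doses, and each expansion adds three subjects.

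**Reproducing the plan's figures.** Base: 5 × 3 = 15, as stated. Maximum = 15 + 3 × (number of units with a DLT).
- Unit = population-by-dose group: 15 + 3 × 5 = 30. This reproduces the stated maximum.
- Unit = milligram dose: 15 + 3 × 2 = 21. This does not.

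**What 30 implies.** Expansions needed: (30 − 15)/3 = 5, so every group has at least one DLT. That is 2 at 20 mg (healthy, CF) and 3 at 50 mg (healthy, CF, *H. pylori*).

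**The two consistent readings.**
- Group throughout: each group ends at 1/6, Table 1 lets it proceed, 30 is reachable and nothing is breached.
- Milligram dose throughout: 2 and 3 DLTs both exceed the 3.2.3 limit of one. Enumerating the possible group orders, with zero or one DLT per group, never reaches 30. The largest total is 21 if a stop halts all enrolment (Table 1's wording) and 27 if it blocks only escalation (3.2.3's wording). With one DLT in all five groups the totals are 15 and 24.

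**A concrete case.** One DLT occurs in healthy subjects at 20 mg and, later, one in CF subjects at 20 mg. By group, each is 1/3 and three CF subjects are added at 20 mg. By milligram dose, two subjects have had a DLT at 20 mg and the CF step from 20 to 50 mg is stopped.

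**Illustration of frequency.** Assume independent subjects, one DLT risk p in all populations, and that a group passes with 0/3, or with 1/3 followed by 0/3. Then q0 = (1−p)³ and q1 = 3p(1−p)² × (1−p)³. The readings diverge when every group at a dose passes but the dose carries two or more DLTs.
- 20 mg, two groups: divergence = q1²; all pass = (q0+q1)².
- 50 mg, three groups: divergence = (q0+q1)³ − q0³ − 3q0²q1; all pass = (q0+q1)³.

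| p | q0 | q1 | 20 mg: divergence / all pass | 50 mg: divergence / all pass |
|---|---|---|---|---|
| 0.05 | 0.8574 | 0.1161 | 0.0135 / 0.9476 = 1.4% | 0.0362 / 0.9224 = 4% |
| 0.10 | 0.7290 | 0.1771 | 0.0314 / 0.8211 = 3.8% | 0.0742 / 0.7440 = 10% |
| 0.20 | 0.5120 | 0.1966 | 0.0387 / 0.5021 = 7.7% | 0.0670 / 0.3558 = 19% |

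The values of p are assumptions; the protocol gives none.

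**The case against.** A reader might infer that the 30-subject scenario simply breaches the protocol's own stopping rule. The text does not support that. The breach needs *dose level* to mean a group in 3.2.1 and a milligram dose in 3.2.3. With the group meaning in both places there is none, and section 1.5 favours that meaning by saying that the same escalation design is used again in CF. Within one population, 5.1.8 pairs cohort and dose one to one, so Table 1 and 3.2.3 count the same subjects.

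Other limits also stand:
- Section 3.2.3 stops dose escalation, not the study; early termination is a separate, discretionary decision of the monitor. As 50 mg is the top dose, a second DLT there affects escalation only if a CF step from 20 to 50 mg is still to come.
- The *H. pylori* group is not an escalation step under 5.1.6, although the figure of 30 includes an expansion for it.
- The monitor sees data daily (8.5), may stop escalation at discretion (3.2) and may set a lower maximum tolerated dose (3.1.3.2), so earlier DLTs remain visible.
- CF subjects have albuterol pre-treatment and a different FEV1 entry criterion, so one shared DLT risk is doubtful.

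These points lower the consequence. They do not define the unit. Section 1.5 does not say how the *H. pylori* group is counted, Table 1 itself uses *dose level* for the milligram dose, and discretion cannot show which written rule applies.

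**Conclusion.** The point holds as inconsistent terminology in a safety stopping rule. One term carries two meanings, and the documents do not settle which applies. On the group reading the maximum is 30 and no rule is broken. On the milligram-dose reading, one DLT per level gives 21, and the 30-subject scenario has 2 DLTs at 20 mg and 3 at 50 mg against a limit of one.

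It would be wrong to conclude that 21 is the correct maximum: on that reading the enumerated ceiling is 21 or 27, depending on whether a stop halts enrolment or only escalation. The counts follow directly from 3.2.1. The percentages are illustrative only, because they rest on assumed risks shared by healthy and CF subjects. The matter should be corrected because the same DLTs can lead to opposite actions. Nothing here bears on which rule is clinically right.

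**What to change.** Reconcile the synopsis, 3.1.3, Table 1, 3.2.1, 3.2.3, 5.1.8 and 9.1 on one counting unit, with *cohort* and *dose level* each defined once. State:
- whether DLTs at the same dose are pooled across populations;
- how the *H. pylori* group is counted, given that 5.1.6 applies Table 1 only to subjects without *H. pylori*;
- whether a stop halts enrolment or only escalation.

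Then restate the maximum enrolment to match. The same edit should align the threshold itself: the synopsis and 3.1.3 refer to more than one additional subject with a DLT, while Table 1 and 3.2.3 refer to more than one subject.

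The sponsor and data safety monitor choose the rule. The cost is protocol wording and possibly a changed maximum, with no added procedures.
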